3.3. Research Approach

3.3.a Research Design Overview. We will conduct a randomized controlled trial, where upon enrollment participants will be randomized to either the *Guerreiras* intervention or to a wait-list control condition, in which participants will also receive the *Guerreiras* intervention after a one-year waiting period. We chose a wait-list control to safeguard ethical treatment of participants by ensuring that a potentially impactful intervention will be available to all after a brief waiting period. Rolling enrollment of 400 participants will take place over one year, with the intervention initiating activities as participants are assigned to a *Guerreiras* group (8-10 participants); group assignment will occur as soon as sufficient participants are enrolled. *Guerreiras* includes five group sessions over the course of 6-8

weeks, led by two peer navigators (PNs). Following group sessions, PNs will provide six months of peer navigation to each participant to support HIV testing (clinic or HIVST), PrEP uptake and persistence, harm reduction and other behavioral prevention as indicated, or HIV care (if participant tests positive). Groups will reconvene for a reunion session 3 months into navigation services (see Intervention Design 3.4). Follow-up data collection for the main

Figure 2: Study Design

trial phase will be conducted every three months, with comprehensive interviewer-administered surveys conducted at enrollment (baseline), 6 months (interim survey), and 12 months (endline), with brief monitoring surveys at the 3-month visits (e.g. 3- and 9-months) to assess prevention uptake (HIV testing, PrEP use, etc; see Figure 2, Study Design). This results in four post-enrollment follow-up visits per participant to document regular prevention uptake and two visits to document changes in stigma measures during the main trial phase. Qualitative interviews will be conducted with 18 participants at two timepoints (36 interviews total) to provide context to our exploration of intersectional stigma and gender affirmation, including how intersectional stigma impacts engagement with *Guerreiras* and HIV prevention uptake, how gender affirming programming impacts intersectional stigma, and insight into psychosocial mechanisms of change over time.

The second phase of the study, the delayed intervention phase, provides an opportunity for the control arm to receive the *Guerreiras* intervention and simultaneously to a) follow intervention arm participants for a further six months to assess the persistence of intervention effects, and b) replicate main trial findings utilizing wait-list control data. Wait-list control participants will be assigned to a *Guerreiras* group for initiation of the full intervention following the main trial and completion of their endline survey. HIV testing will be monitored through clinical records at partnering services, through PN forms on HIVST distribution, and through monitoring visits every 3 months. PrEP initiation and persistence will be monitored using the national medications dispensing system (SICLON), which is utilized in all public clinics. Dried blood spots (DBS) testing will assess drug levels among those on PrEP to measure of adherence and collected at clinic visits for PrEP dispensation. Comprehensive surveys measuring stigma domains will occur at 6-month intervals (see Measures 3.7).

3.3.b Study Setting and Population

Study setting. The proposed study will take place in the São Paulo metropolitan area in Southern Brazil in collaboration with the Santa Casa School of Medical Sciences (*Faculdade de Ciências Médicas da Santa Casa de São Paulo*). São Paulo is the largest city in Latin America, among the first to document HIV among LGBTI

communities, and both a global leader in equity of HIV treatment and a world center for gender transition care. The Brazilian investigative team has run a number of large state-funded surveys of the local transgender population, and has established the NIH-funded Trans*National Cohort (R01MD010678), an open cohort of trans women recruited through respondent driven sampling (RDS)⁷⁸. [name] (site PI) has established relationships with a broad network of stakeholders, including public health and social services most frequented by the trans community and with the State HIV care reference and training center (CRT). The CRT includes a large outpatient clinic for HIV/AIDS (4000 patients currently in care), a small hospital, day-clinic, laboratory, HIV counseling and testing (HCT), a sexually transmitted infection (STI) clinic, and a prevention and research unit. CRT is also in charge of the HIV surveillance system for the state of São Paulo. Importantly, CRT is home to the largest and more comprehensive outpatient clinic for transgender health in the country and is the clinical research site for the Trans*National cohort and the Trans Amigas study (R34MH112177) of peer navigation for HIV-positive trans women. Procedures and activities for the proposal study will occur at the CRT and at SAE Campos Elíseos, which is the public health facility in central São Paulo catering to a large trans population. HIV testing, care and treatment, and PrEP are available at both clinic locations; participants who seroconvert will also be referred to one of these facilities for treatment. (see Letters of Support from State and Municipal Secretaries of Health and Trans*National). Finally, to ensure that participants who prefer not to engage with those specific clinic facilities also can participate, activities will also occur at the NUDHES community research office in central São Paulo. The easily accessible NUDHES space is home to a variety of NGOs and CBOs working with vulnerable populations (LGBT+, migrants, black communities) on social inclusion programming.

Study population. The target population is adult trans women in the São Paulo metropolitan area. Despite Brazil's progressive laws supporting LGBTI populations, including constitutional sanctioning of same-sex marriage, the right to change one's legal name according to gender identity, and the codified universal right to healthcare, research in Brazil has confirmed trans women's extreme vulnerability to violence, substance use, stigma and discrimination⁷⁹, with limited access to public health and social services^{80,81}. Many trans women in Brazil also engage in sex work, in part as a result of the difficulty in finding other work due to stigma and high levels of social vulnerability in terms of education and socio-economic status^{31,81-84}. Recent findings from Projeto Muriel, a large survey of trans populations in São Paulo by [name], indicate that 86.8% of trans women have experienced discrimination for being trans women, particularly from family (70.1%), in employment (63.9%), by police (57.7%), and by health providers (47.4%). We aim to enroll a broad cross-section of trans women who mirror the demographics of the metropolitan area of São Paulo, approximately half of whom we will recruit from the Trans*National cohort and half from clinical services and outreach events.

3.4. Intervention Design.

3.4.a Overview. *Guerreiras* is a multi-level (group- and individual-level) intervention to improve engagement in the HIV prevention continuum among trans women in Brazil by addressing intersectional stigma, specifically identity-based stigmas related to gender identity and race, stigmas based on social position, e.g. engagement in sex work and substance use, and stigma-related barriers, specifically HIV and PrEP stigma. The group-level component of *Guerreiras* is facilitated by two peer navigators (PNs) and consists of 5 sessions conducted over 6-8 weeks. To address HIV stigma, one PN will be living with HIV and the other will be HIV-negative. Group content (see Table 2) is informed by gender affirmation theory and designed to address intersectional stigma through building gender pride (reducing internalized stigma), role modeling (reducing HIV and PrEP stigma), and empowering participants to access healthcare by problem-solving anticipated stigma and effectively responding to enacted stigma (increasing stigma resilience). Following the group sessions, the individual-level component of *Guerreiras* consists of 6 months of peer navigation to support HIV prevention uptake including HIV testing (clinic-based or self-testing), PrEP, or HIV care (if participant tests positive during the intervention), and harm reduction services for those for whom these services are indicated. The six months of peer navigation re-affirm strategies learned during group sessions in one-on-one navigation sessions, with a reunion group session 3 months into navigation, which provides an opportunity to share experiences collectively.

Table 2. *Guerreiras* intervention content

Session	Topic	Objectives
1	Gender Pride / Orgulho Trans	Explore and discuss trans identities and history in Brazil Discuss gender pride, identify positive role models to combat internalized stigma Introduce HIV self-testing and PrEP in relation to the concepts of self-care, self-worth, and sexual health
2	Looking Good, Feeling Good / Sou Bonita Meu Bem, e Daí?	Discuss gender affirmation, its effect on self-image, self-care, empowerment to cope/respond to enacted stigma Discuss transition-related health care (i.e. hormone use/access, dangers of and safer injection silicone practices) Empower access to gender affirming healthcare, including HIV testing, PrEP, or engagement in HIV treatment Explore relationship between physical health (e.g., nutrition, sleep, HIV testing) and feeling good about oneself

3	Let's Talk About Sex / Vamos Falar Abertamente Sobre Sexo	Provide information on HIV rates and risk factors among trans women in Brazil Discuss self-protection in the context of gender affirmation, including HIV testing and PrEP Discuss the importance of knowing one's HIV status and getting treatment if positive Empower access to HIV testing and treatment services; discuss barriers to HIV testing and treatment, such as anticipated stigma and/or previous experiences of enacted stigma, and coping strategies (e.g. HIV self-testing)
4	Taking Back the Power / Dando a Volta por Cima	Discuss how trans-related stigma impacts one's sense of personal power, explore ways to reclaim one's power to confront stigma Explore assertiveness skills, practice communicating with healthcare providers to challenge structural and interpersonal enacted and anticipated stigma
5	Surviving and Thriving / Sobrevivendo e Crescendo	Discuss how knowing one's HIV status and getting tested and/or treatment for HIV is vital to self-care Discuss healthy ways of coping with transphobic stigma in relationships and the stress of sex work Consider the effect of substance use on one's sexual health; offer harm reduction resources and support Celebrate trans community as a vital source of social support Reinforce gender pride to resist internalization of intersectional stigma
Reunion (3 mos after session 5)	Living Your Power / Vivendo o Seu Poder	Explore ongoing self-care strategies, including gender affirmation, regular HIV testing and/or PrEP persistence Review assertiveness skills and discuss experiences communicating with health care providers to challenge structural and interpersonal enacted and anticipated stigma Reinforce gender pride to resist internalization of intersectional stigma
Navigation (for 6 mos post-groups)	Staying Connected / Permanecendo Ligada	Provide one-on-one individualized support for navigating current healthcare system, reinforcing concepts from group work, including problem-solving and strategies for coping with anticipated and enacted stigma

3.4.b. HIV self-testing and/or navigation to clinic-based testing. HIV self-testing (HIVST) will be introduced and demonstrated in session 1 and will be made consistently available to all *Guerreiras* participants for free through our public sector partnerships. HIVST is available in Brazil in the public sector⁸⁵. PNs will bring HIVST kits to each session; *Guerreiras* participants will have the option of utilizing HIVST in groups, with their PN, or on their own. At each group session participants will be invited to debrief their HIVST experience with the group if they so choose. PNs will offer one-on-one support for HIVST before and after each group session as needed and will offer navigation to clinic-based HIV testing to those who prefer clinic-based testing. PNs will be trained in test counseling to ensure they are prepared to debrief test results, though very few social harms have been reported in HIVST studies with vulnerable populations^{71,86,87}. PNs will record HIVST distribution and tests conducted with them or in the group on standardized case report forms (see section 3.6.e).

3.4.c. PrEP uptake, persistence, and adherence support. The most important indication for PrEP use is an expressed desire to use PrEP⁸⁸. PNs will provide PrEP education and navigate participants to obtain PrEP upon request. PrEP uptake, persistence, and adherence support focus on empowering personal choice, self-assessment of HIV risk, desire for feeling safe during sex, and daily habit formation. Group sessions include a trans-specific personal HIV risk assessment and PrEP decision-making tool developed specifically for trans women. PrEP-related group session content focuses on documented key facilitators of persistence and adherence, including: 1) daily habit formation; 2) knowledge that PrEP is highly effective when used; 3) disclosure of PrEP use to housemates who may discover the medication; 4) making plans for travel and substance use; 5) information about safety, including lack of known PrEP drug interactions with feminizing hormones²¹; 6) clear information that PrEP can be taken with or without food, at any hour, and with alcohol; and 7) information about the flexibility of the regimen including that forgotten tablets should be taken when remembered (even if late), that a tablet should be taken if one is not sure that the scheduled tablet was taken, and that PrEP is highly protective even if occasional doses are missed (i.e. don't panic if you miss a dose)^{19,89}.

3.4.d. Ensuring a tailored prevention plan. While supporting PrEP uptake and persistence is urgent for trans women as a key population at high risk for HIV, PrEP will not be indicated for a small subset (~5-10%) who have clinical contraindications and/or low risk. Integral to *Guerreiras* intervention content and with support from PNs, participants will learn to accurately self-assess their HIV risk, options for accessing HIV prevention tools and support, and will adopt a prevention strategy tailored to their specific needs and preferences, e.g. HIV testing (clinic- or self-testing), PrEP, and/or behavioral risk reduction, such harm reduction or condom use.

3.4.e. Peer navigator training: Our team of investigators is experienced in staffing, training, and supervising clinical and behavioral intervention trials. We will identify and intensively train twenty potential peer navigators (PNs). Among these, 16 will be selected based on fit for facilitating the intervention. All PNs will be trans women, half will be living with HIV and currently receiving HIV care, and half will be HIV-negative and utilizing HIV prevention tools. PNs will be paired to ensure mixed status navigation teams to provide role modeling for HIV prevention and treatment, as well as to address HIV-related stigma for those who seroconvert or avoid testing due to fear of a positive result. PNs will be identified through stakeholders, clinics, and CBO partners as well as through NUDHES, a successful approach for identifying PNs for the Trans Amigas project.

The multi-week PN training will adapt detailed manuals we developed for facilitating the Sheroes group sessions and conducting peer navigation in Trans Amigas. For the group-level component, PNs will acquire skills in group facilitation through coaching, role plays, and mock sessions. HIV-related training content will include personalized HIV risk assessment, HIV test counseling (including HIV self-testing), PrEP, and HIV treatment. Stigma-related training content will include the concepts of intersectional stigma and gender affirmation, with a focus on the types of stigma targeted by the intervention (identity, social position, and barriers) and building stigma resilience through coping skills (e.g. coping with anticipated and enacted stigma) and empowerment. For the individual-level component, PNs will be trained on the role of a PN, providing support to participants in developing a personalized HIV prevention plan, fostering an alliance, and ethical behavior, including maintaining appropriate personal/professional boundaries. PNs will learn about interactions they will have with participants (e.g., in-person meetings, phone calls, text messages) and how to record them (see 3.6e for intervention monitoring), assessing participant needs, and strategies for addressing routine and more challenging barriers to prevention and care. To learn about potential resources for participants, PNs will tour trans-friendly service agencies in São Paulo, including the LGBT Citizenship Center, the Alcohol and Drugs Psychosocial Care Center, NGOs providing harm reduction support, the Racial and Intolerance Crimes Police Station, and the Social Assistance Reference Center. PNs will meet with the study coordinator weekly to conduct case conferences, receive support, and problem-solve. The study coordinator will have biweekly calls with investigators to discuss issues and strategize solutions. Refresher trainings will be conducted regularly to improve facilitation and navigation skills, to train new PNs if staff turnover occurs, and to address challenges.

3.5. Participant Eligibility, Recruitment, Randomization, Retention.

3.5.a. Eligibility: Participants must be 18 years or older; assigned ‘male’ at birth but currently identify as female, transgender, transsexual, or *travesti* (a common term for trans women in Brazil); not be known to be HIV positive; be a resident of the São Paulo area; and consent for study procedures, including review of clinical records. In Brazil, language that trans women use to describe themselves includes cultural terms such as ‘*transsexuais*’, ‘*mulher trans*’, and ‘*travesti*’ among others. No restrictions will be placed on the degree to which the participant has transitioned legally or physically. Participants may be PrEP-naïve or have initiated PrEP; being on PrEP is not an exclusion criterion. While we do not anticipate encountering many trans women already taking PrEP, preliminary data indicate that a large proportion of trans women who initiate PrEP will struggle with persistence and require renewed engagement¹⁹. Based on current data, we expect a maximum of 5% to have initiated PrEP prior to enrollment. We will not require HIV testing to enter the study; any participant who enrolls and either discovers she is positive or seroconverts will remain enrolled with navigation focused on HIV treatment. Recruitment staff will use a brief screening tool to establish eligibility prior to enrollment.

3.5.b. Recruitment: Participants will be recruited from three sources over the course of 6 months: (1) those currently enrolled in the Trans*National Cohort in São Paulo; (2) trans women presenting for services at partnering clinics or presenting for HIV testing through the clinic run community-based programs; and (3) trans women recruited through targeted recruitment events. The Trans*National Cohort Study utilizes respondent-driven sampling (RDS) and has enrolled 565 HIV-negative women. Any participants not known to have seroconverted in the cohort will be invited to participate in *Guerreiras*. We expect to recruit approximately half of the participants through this method. We will also invite trans women testing negative for HIV at either SAE Campos Elíseos, the CRT, or through the community-based testing programs run by CRT to participate. The community-based testing program, called “Fique Sabendo” or “be in the know” is a state-run operation that visits areas where trans women work and congregate for testing. Finally, we will conduct recruitment events, advertised through trans-friendly locations, the PN team, and through social media, to ensure we reach trans women not seeking services or already in Trans*National. We aim to enroll half of the study participants through clinic partners and outreach events. (for details see Form E, Recruitment and Retention).

When a potential participant is interested in the study, staff will screen and enroll them, provide an appointment for screening and enrollment, or record preferred contact information to schedule an appointment. All participants will provide informed consent for study procedures, including clinical record extraction and PrEP eligibility exams (e.g. HIV and creatinine) if interested in PrEP, per national guidelines (see Human Subjects).

3.5.c. Randomization: Participants will be randomly assigned 1:1 to one of two arms using a computer generated “random order of assignment” list such that 200 will be assigned to the intervention arm and 200 will be assigned to the wait-list control arm. The random assignments will be placed in advance in sealed, numbered envelopes in each study location. To avoid potential bias based on timing or location of enrollment, we will use “block randomization,” with randomly-permuted block sizes to avoid identification of the allocation

of the last participant in a block. For participants allocated to intervention, assignment to a *Guerreiras* group will occur as soon as there is sufficient enrollment to form a group.

3.5.d. Retention: Upon enrollment, participants will be asked to provide contact information, including address, cell phone/WhatsApp number, other social media contacts, and also to volunteer up to three individuals who can contact them should study staff be unable to do so. At each 3-month monitoring visit, staff will validate contact information in addition to completing data collection (see section 3.6.a & 3.6.b). The Brazilian study team has experience with these contact methods in retaining Trans*National and Trans Amigas study participants. (See Form E, Recruitment and Retention for further details on retention plans). Given the mobility and often unstable housing trans women experience, we expect to retain 75% of the cohort. To date just over 50% of Trans*National participants (an observational study) and just over 80% of Trans Amigas participants (an intervention study with consistent contact) have been retained; as a result, we believe retention will be closer to Trans Amigas retention rates. We account for attrition in the statistical power (see section 3.8).

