HIV self-testing among trans women. We have extensive experience introducing HIV self-testing (HIVST) for populations who may experience HIV stigma-related barriers to accessing clinic-based testing, including conducting the first U.S. study among trans women¹³ and early HIVST research with MSM in Brazil^{14,15,18}; all demonstrating high levels of acceptability. Further, [name] research has established that access to HIVST improves HIV testing frequency among at-risk populations^{17,65} and that peer-based distribution of HIVST is an efficacious, safe, and acceptable approach for disseminating test kits^{17,16,65}. (Table 1) Following the 2017 release of the WHO *Guidelines on HIV Self-Testing and Partner Notification*⁷¹, the Brazil approved the first HIV self-test for sale in pharmacies. In 2018 the government announced availability of HIVST through SUS, aiming to increase testing uptake for those less likely to access testing or who test less frequently than recommended, including transgender women⁷². The locally manufactured DPP HIV 1/2 Rapid Assay can use blood or oral fluid samples and has been successfully utilized by key populations in Brazil⁷³. Important to this application, HIVST has been found to be a feasible and acceptable method of increasing PrEP persistence among sex workers by eliminating stigma-related barriers to routine HIV testing required during PrEP use⁷⁴.

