3.6.b PrEP Data Extraction: Data regarding PrEP use, which became available nationally for at-risk populations in December 2017, will be extracted from the national SICLOM (Sistema de Controle Logístico de Medicamentos) database, which captures all ARV distribution nationally. PrEP dispensing will be extracted quarterly from SICLOM and stored securely, including visit dates, pill count and dose, and any associated observations. We will utilize clinical records at the facilities to note visits for other purposes, including visits related to PrEP side effects (see 3.6.c below). The investigators have successfully utilized SICLOM for extraction of medication dispensing information in the Trans Amigas project.

3.6.c Clinic data extraction: Clinic-based HIV testing data and uptake of clinic-based prevention services, including STI testing and treatment, sexual health counseling, and HIV care visits (for those who seroconvert) will be extracted bi-annually, including visit purpose, dates, services received, HIV test result, and associated observations. Data from participant clinical files will be extracted electronically and uploaded to a secure data base kept by the study data managers (see Form E Human Subjects for details). Our team has successfully and safely extracted clinical data for Trans Amigas participants at the CRT and will utilize similar protocols.

3.6.d Drug Concentration Testing: Drug concentrations in the blood have emerged as strong correlates of protection in PrEP trials, accounting for the majority of the variation in PrEP benefits. Dried blood spots (DBS) are easy to collect, require no processing in the field, are easy to store and ship, and are feasible for monitoring drug concentrations among trans women in our current PrEP demonstration project. The DBS will be collected at the clinical sites at each visit for PrEP dispensation by trained staff and processed in accordance with procedures developed for previous studies. (Investigators have all utilized DBS for drug concentrations in previous studies). Staff will use a medium gauge lancet to puncture the fingertip and extract

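### The delayed phase cannot replicate the randomised comparison, because no untreated randomised arm remains; any change in the wait-list arm is open to time trends in PrEP and self-testing

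*Combined protocol and SAP*

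**What the plan says.** Section 3.3.a gives the delayed phase two scientific purposes. One is to "follow intervention arm participants for a further six months to assess the persistence of intervention effects". The other is to "replicate main trial findings utilizing wait-list control data". The same section describes what happens to the controls: "Wait-list control participants will be assigned to a *Guerreiras* group for initiation of the full intervention following the main trial", and, in the design overview, "participants will also receive the *Guerreiras* intervention after a one-year waiting period".

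Section 3.8 restricts the planned between-arm GEE comparison to the main trial phase. For replicability it gives no comparator, contrast or model, and refers the reader to Form E, Statistical Design and Power.

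Two statements bear on the background. Section 3.6.b: "Data regarding PrEP use, which became available nationally for at-risk populations in December 2017". Section 3.1.b: "In 2018 the government announced availability of HIVST through SUS, aiming to increase testing uptake".

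The enrolment period is given twice, differently. Section 3.3.a: "Rolling enrollment of 400 participants will take place over one year". Section 3.5.b: "Participants will be recruited from three sources over the course of 6 months".

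**The concern.** A replication of a randomised finding needs a second contrast protected in the same way as the first. In the delayed phase one arm is being treated and the other has finished treatment. Whatever contrast is built from wait-list data, nobody at the same time since enrolment is both randomised and untreated.

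The obvious remaining contrast sets the delayed phase of the wait-list women against their own waiting year. That contrast takes in anything that changes over calendar time. The two primary outcomes, HIV testing and PrEP use, both depend on tools that the protocol describes as recently introduced in the public system. If supply, awareness or outreach grows between the two years, the growth enters the estimate as effect. A result labelled as replication would be read as a second confirmation of the trial, which it could not be.

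**Working it through.** **1. Who is untreated, and when.**

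| Period (time since enrolment) | Intervention arm | Wait-list arm |
|---|---|---|
| Main trial, months 0-12 | treated | untreated |
| Delayed phase, after month 12 | already treated, followed 6 more months | treated |

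Only the first row contains a randomised treated-versus-untreated contrast. No analysis in Form E can create one in the second row.

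**2. The plan's own figures.** The plan states no figure for the replication. Its main-phase detectable differences (section 3.8) are 13 points for testing from 50% and 8 points for persistent PrEP use from 5%. They assume 300 analysed (150 per arm), four measurements, alpha .05 and power .80. The within-person correlation rho and the peer-navigator ICC are not given. Without clustering, rho=.5 gives 12.7 and 7.1 points, and rho=.6 gives 13.4 and 7.7. The stated figures are therefore attainable, and they serve here only as a yardstick.

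**3. One interval before and one after, no intervention effect.** Inputs: n = 200 × 0.75 = 150 wait-list completers; starting proportions from section 3.8; assumed drift; assumed latent (bivariate normal) correlation .5 or .8; exact McNemar test at two-sided .05, counted only when favourable. Discordant probabilities are P(no→yes) = p1 − p11 and P(yes→no) = p0 − p11, where p11 is the probability of yes in both periods.

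| Background change | Correlation | no→yes | yes→no | Declared a gain |
|---|---|---|---|---|
| PrEP 5%→10% | .5 | .081 | .031 | 37% |
| PrEP 5%→10% | .8 | .065 | .015 | 50% |
| Testing 50%→60% | .5 | .220 | .120 | 51% |
| Testing 50%→60% | .8 | .159 | .059 | 70% |

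These are exact sums over the discordant pairs. Simulation gives the same within its error (36-50% and 50-71%). With zero drift the rate is 1-2%, so the excess comes from the drift.

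**4. Four visits before and four after.** Surveys in the delayed phase imply about a year of quarterly visits for wait-list women. With exchangeable rho, s = p(1−p) and f = (1+3·rho)/4:

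SE² = [f·s0 + f·s1 − 2·rho·√(s0·s1)] / 150.

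PrEP 5%→10%, rho=.5: f = .625; SE² = (.625×.0475 + .625×.09 − √(.0475×.09))/150 = .0206/150; SE = .0117; z = .05/.0117 = 4.27; probability of significance Φ(4.27−1.96) = 99%.

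| Background change | rho .2 | rho .5 | rho .8 |
|---|---|---|---|
| PrEP +3 points | 65% | 82% | 98% |
| PrEP +5 points | 95% | 99% | >99% |
| Testing +5 points | 49% | 69% | 97% |

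Drifts well below the planned 8 and 13 points would usually, or about half the time at the lowest rho for testing, be declared an effect. Clustering by navigator pair is ignored; allowing for it would lower these percentages.

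**5. How much concurrent waiting time exists.** Suppose enrolment is uniform over E months and each control crosses over at her own month 12. The first crossover is at calendar month 12. A control enrolled at month u then has u of her 12 waiting months after that point. The mean share is (E/2)/12: 6/12 = 50% for E = 12, and 3/12 = 25% for E = 6. If instead all controls wait until the main trial as a whole has ended, the overlap is little or none.

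**The case against.** The strongest reply is that the method has not been seen. Section 3.8 places the replicability analysis in Form E, and nothing supplied says that it is a before-after comparison. A reader might infer that the plan commits to an uncontrolled before-after test; the documents do not support that. They support a narrower statement: the aim is worded as replication, and the supplied text names no comparator and no handling of time trends. That part of the reply stands, and it makes the bias conditional.

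Second, rolling enrolment may stagger the crossover, so that later-enrolled controls are still waiting when earlier ones start. A calendar-adjusted comparison could then be made for part of the data. This also stands, provided crossover is individual. The phrase placing crossover after the main trial leaves that unclear.

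Third, no background trend is documented. A recent roll-out does not prove a rise: section 3.1 reports only 74 trans women nationally starting PrEP through the public system by August 2018, which could equally suggest stagnation. The percentages above therefore illustrate sensitivity and do not predict an outcome.

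A reader might also infer that analysing women retained through the waiting year inflates the result. It does not by itself: in a paired comparison the same women supply both periods, and section 3.8 plans multiple imputation for incomplete data.

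Finally, replication is not one of the stated aims, and the randomised tests for Aims 1 and 2 are untouched. That stands, and it limits the weight of the point.

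**Conclusion.** The concern holds in a limited form. Whatever Form E contains, the delayed phase has no concurrent untreated randomised arm, so its result cannot replicate the randomised contrast or confirm it independently. Whether it is also biased by time trends depends on the unseen method. If it is an unadjusted before-after change in 150 completers, assumed drifts of 5 points in PrEP and 10 points in testing would be declared gains in about 36-50% and 50-71% of cases with one interval per period, and in at least 95% and 97.5% with four. These figures rest on assumed drift and correlation. The point concerns a secondary analysis and what may be concluded from it; it should be corrected, but it does not threaten the primary comparison.

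**What to change.** - In section 3.3.a, describe the result as a non-randomised within-arm change in the wait-list arm, and state that it is neither a replication nor independent confirmation of the randomised effect.
- State the contrast and model in the protocol. Include calendar quarter, use not-yet-treated wait-list time where it exists, and report the slope within the waiting year beside the estimate. If Form E already adjusts for calendar time, bring that text forward.
- Reconcile the one-year and 6-month enrolment periods in sections 3.3.a and 3.5.b, and say whether crossover follows each woman's own month 12 or the end of the main trial as a whole. These decide whether the concurrent share is about 50%, about 25% or close to none.

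No new data are needed, since visit and dispensing dates are already collected. The cost is wider intervals and a weaker claim. One limit remains: treated wait-list women are always further from enrolment than waiting ones, so calendar adjustment does not separate treatment from time since enrolment, including any effect of repeated surveys.
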